- The participant will be shown the individual components of the VR system (View-Master with smartphone inserted; external speaker for audio projection; monitor for study staff to observe what the participant is experiencing), be given instructions on how to use the device and encouraged to ask questions.
- Once the participant indicates she or he is ready, they'll be asked to begin the VR experience. Study personnel will stay in the room with the participant for the entire duration and will be viewing on the monitor what the participant is experiencing virtually. Study personnel will provide guidance and answer questions regarding the technology and its use but will not answer questions regarding the facilities, prep, procedure or recovery (this will be explained prior to starting the VR experience).
- When the participant indicates she or he is finished with the VR experience and has had a few minutes to orient, the wellness self-assessment will be administered again.
- Participants will be thanked for their participation (and provided a gift card) and remaining study activities will be reviewed.

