### ***Visit 2 – Procedure Day***

Study personnel will meet participants in their Prep/Recovery room prior to their procedure and the STAI assessment will be administered to all. A Retrospective Wellness questionnaire will be administered to the VR intervention group only in order to assess for any longer-term adverse effects (e.g., headache lasting several hours) of the VR experience. Postprocedure, a patient preparedness survey will be administered to all participants. All participants will again be thanked for their participation, all questions will be answered and their study participation will conclude.

All of the above activities except for standard procedural education will be research related. The average study participation time frame for all participants will be less than 1 month.

The data collected for this study entails the State-Trait Anxiety Inventory results, wellness self-assessments results, preparedness survey results and meta-data results.

e. Data Management

The data collected for this study will comprise of survey results (State-Trait Anxiety Assessment; VR related wellness assessments; and a preparedness assessment) as well as demographic and medical history data (for general reporting purposes). The data will be collected directly from participants using paper tools, where after the responses will be entered into an electronic data capture (EDC) system. The study EDC will be housed on secure Spectrum Health servers and the paper documents will be stored in secure Spectrum Health facilities.

f. Withdrawal of Subjects

Participants may change their minds at any time and choose to withdraw from this study; however, there are no circumstances under which participants would be withdrawn without their consent.

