## 10. Risks to Subjects

Possible documented risks to using virtual reality include seizures; loss of awareness; eye strain; eye or muscle twitching; involuntary movements; altered, blurred, or double vision or other visual abnormalities; dizziness; disorientation; impaired balance; impaired hand-eye coordination; excessive sweating; increased salivation; nausea; lightheadedness; discomfort or pain in the head or eyes; drowsiness; fatigue; and/or motion sickness.

About 1 in 4000 may have severe dizziness, seizures, eye or muscle twitching or blackouts triggered by light flashes or patterns, and this may occur while they are watching TV, playing video games or experiencing virtual reality, even if they have never had a seizure or blackout before or have no history of seizures or epilepsy. Such seizures are more common

in children and young people under the age of 20. These risks are generally associated with prolonged use and with the complete VR systems which entail large, fitted headsets and full body utilization. The VR hardware being used for this study is a reductive version (a hand-held View-Master with a smartphone), the participants will be seated for the duration and the experiences will last 10-15 minutes. The participant will be in complete control and can set down the View-Master at any time as well as choose to discontinue the experience.

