### **Post VR Experience Wellness Self-Assessment**

Please identify if you are currently experiencing any of the following and rate the degree of severity of the symptom(s) on a scale from 1 (mild) – 5 (severe):

1. Headache:

No       Yes

1                    2                    3                    4                    5

2. Altered/Blurred/Double Vision:

No       Yes

1                    2                    3                    4                    5

3. Nausea:

No       Yes

1                    2                    3                    4                    5

4. Dizziness/Disorientation:

No       Yes

1                    2                    3                    4                    5

5. Fatigue:

No       Yes

1                    2                    3                    4                    5

Subject ID:

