### **Retrospective VR Experience Wellness Self-Assessment**

Please identify if you recall any of the following within 24 hours after your VR experience and rate the degree of severity of the symptom(s) on a scale from 1 (mild) – 5 (severe):

1. Headache:

No       Yes

1                    2                    3                    4                    5

2. Altered/Blurred/Double Vision:

No       Yes

1                    2                    3                    4                    5

3. Nausea:

No       Yes

1                    2                    3                    4                    5

4. Dizziness/Disorientation:

No       Yes

1                    2                    3                    4                    5

5. Fatigue:

No       Yes

1                    2                    3                    4                    5

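### No wellness form asks about symptoms during the VR exposure itself, so a symptom that settles before the post-VR form is recorded as absent on the day

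*Combined protocol and SAP*

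**What the plan says.** Participants randomized to VR complete three wellness self-assessments (section 8d; Appendix C, Wellness Self Assessments). Each covers the same five items: headache, vision, nausea, dizziness or disorientation, and fatigue. Each item is No/Yes with a 1-5 severity rating.

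- The Pre form is given before VR and asks about the present moment.
- The Post form is given when the participant says VR is finished and "has had a few minutes to orient, the wellness self-assessment will be administered again". Its instruction is "Please identify if you are currently experiencing any of the following".
- The Retrospective form is given on the procedure day, with the instruction "Please identify if you recall any of the following within 24 hours after your VR experience". Section 8d gives its purpose as "in order to assess for any longer-term adverse effects (e.g., headache lasting several hours) of the VR experience".

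On the exposure, section 10 states that "the experiences will last 10-15 minutes" and that "The participant will be in complete control and can set down the View-Master at any time as well as choose to discontinue the experience". Section 8d adds: "Study personnel will stay in the room with the participant for the entire duration and will be viewing on the monitor". Their stated tasks are to guide the participant and answer questions about the technology. Recording symptoms or early stopping is not among them.

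Section 8c names anxiety as the primary outcome and preparedness as a secondary analysis. Section 9b describes no analysis of the wellness data.

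**The concern.** Section 10 lists nausea, dizziness, disorientation and visual abnormalities among the possible risks of VR, and the forms ask about these. The aim is evidently to learn how well VR is tolerated. Yet the forms cover the time before exposure, a point some minutes after it, and the following 24 hours. The exposure is left out.

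A participant who is dizzy while viewing and well after the pause answers the Post form correctly with No. A participant whose symptom has eased but not gone reports its current severity, not its worst. If VR is stopped early because of a symptom, no form says so, and a short session from intolerance looks like a short session by choice.

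What is at stake is the description of acute tolerability that would accompany the anxiety result. Section 11 says no benefit of VR before a procedure is yet known, so a sound tolerability record would matter to anyone deciding whether to offer it. The reason for stopping would also help show how much of the intervention was received.

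**Working it through.** **The plan's own figure.** The only stated design figure is 86 per group (section 9a). For a two-sided, two-sample t-test with effect size 0.5, alpha 0.05 and power 90%, the noncentral t calculation gives 85.03, rounded up to 86; power at 86 per group is 0.903. The figure reproduces. It concerns anxiety and does not depend on the wellness forms.

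**The forms side by side.**

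| Form | When given | Period asked about | During VR? | Early stop? |
|---|---|---|---|---|
| Pre | Before VR | Present moment | No | No |
| Post | After VR and an untimed pause | Present moment | No | No |
| Retrospective | Procedure day, by recall | 24 hours after VR | No | No |

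**Tracing a during-VR symptom by when it ends.**

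1. Still present when the Post form is given: recorded, at its current severity.
2. Lasts past the end of viewing but settles in the pause: No on the Post form. It falls inside the Retrospective window, so it may be recovered if remembered. Section 8d gives average participation as under 1 month, so recall may be days or weeks later.
3. Ends while the participant is still viewing: No on the Post form, and before the Retrospective window opens. No form's wording covers it.

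**Direction and size.** Let p be the proportion of VR participants with a given symptom during VR, a the share of those cases ending during viewing, b the share settling in the pause, and c the share of the latter recalled at Visit 2.

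- Proportion recorded on the Post form = p × (1 − a − b).
- Share of true cases missed on the day = a + b.
- Share missed on both forms = a + b × (1 − c).

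Both missed shares are zero or positive, so for these symptoms the error runs only one way. If a = b = 0, nothing is missed. If a + b = 1, the Post form records none. The documents give none of p, a, b or c, so any value between 0 and 1 for the missed share would simply restate the assumption put in.

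**The case against.** The case against is substantial, and much of it stands.

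- **Like-for-like design.** Letting momentary disorientation pass and then repeating the Pre form's wording is defensible. This stands: the present-moment question should stay, and what is missing is a further item.
- **The Retrospective form.** It covers symptoms that persisted into the pause. This stands in part: it narrows the gap, but it relies on recall, is aimed at longer-term effects and does not ask about the exposure.
- **Staff presence.** Stopping or visible distress would probably be seen, and section 8d lists undefined metadata that might include session length. But nothing directs staff to record symptoms or reasons for stopping, so observation need not become data.
- **Low expected rates.** Section 8b excludes people with seizures, migraine or severe motion-sickness susceptibility. Section 10 describes seated use of simple hardware for a short time. This is a fair reason to expect few events, though the present forms cannot confirm it.

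A reader might also infer three stronger claims that the documents do not support.

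- **That the poorest tolerators are the most likely to be missed.** The pause begins when the participant says VR is finished, and nothing shows that early stoppers wait longer. Someone who stops at symptom onset may have a shorter gap to the form than someone who feels ill at minute 4 and views to minute 15, which adds 11 minutes.
- **That a planned before-and-after wellness comparison is biased.** Sections 8c and 9b plan no such comparison.
- **That the understatement can be given as a percentage.** The documents supply no symptom rate and no settling share.

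**Conclusion.** The point holds as a gap in safety data capture. Followed as written, the plan records as absent on the day any during-VR symptom that has settled by the Post form. Symptoms that reached the pause may be partly recovered at Visit 2; those that ended during viewing fall outside every form's wording, unless a participant reads the Retrospective question loosely. Early stopping because of a symptom is not captured.

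For such symptoms the error can only run toward better tolerability. Its size is unknown and is zero if nothing settles before the form. The conclusion rests on the wording and timing of the forms and on the absence of any recording instruction to staff, not on an assumed event rate. Wellness is not a named endpoint, and the primary comparison and the 86 per group stand. This is a worthwhile inexpensive improvement, not a flaw in the main result.

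**What to change.** Keep the present-moment question on the Post form, so that it stays comparable with the Pre form and with data already collected. Then:

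- For each of the five symptoms, add: *At any time during the VR experience: No / Yes, worst severity 1-5*.
- Add one line: *Did you stop the VR early because of a symptom? No / Yes, which*.
- Report both descriptively (counts and worst severity) alongside the existing wellness data, stating how many participants completed the revised form.

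The cost is an amendment to one existing form and its electronic data capture fields, with no added staff, visit or procedure. The downside is that section 8d shows enrolment already under way (randomization moved to REDCap for the rest of the study), so the new items would come only from participants enrolled after the change. For earlier participants the report should say that symptoms during VR were not asked about.

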### ***Visit 2 – Procedure Day***

Study personnel will meet participants in their Prep/Recovery room prior to their procedure and the STAI assessment will be administered to all. A Retrospective Wellness questionnaire will be administered to the VR intervention group only in order to assess for any longer-term adverse effects (e.g., headache lasting several hours) of the VR experience. Postprocedure, a patient preparedness survey will be administered to all participants. All participants will again be thanked for their participation, all questions will be answered and their study participation will conclude.

All of the above activities except for standard procedural education will be research related. The average study participation time frame for all participants will be less than 1 month.

The data collected for this study entails the State-Trait Anxiety Inventory results, wellness self-assessments results, preparedness survey results and meta-data results.

e. Data Management

The data collected for this study will comprise of survey results (State-Trait Anxiety Assessment; VR related wellness assessments; and a preparedness assessment) as well as demographic and medical history data (for general reporting purposes). The data will be collected directly from participants using paper tools, where after the responses will be entered into an electronic data capture (EDC) system. The study EDC will be housed on secure Spectrum Health servers and the paper documents will be stored in secure Spectrum Health facilities.

f. Withdrawal of Subjects

Participants may change their minds at any time and choose to withdraw from this study; however, there are no circumstances under which participants would be withdrawn without their consent.

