### **c. Study Endpoints**

The primary measure of interest in the present study is patient anxiety, as measured using the State Trait Anxiety Inventory (2, 3).

In all patients, anxiety will be assessed using this tool at baseline (prior to randomization) and again on the day of the procedure, just prior to undergoing catheterization.

The primary outcome of this study is the anxiety level measured just prior to catheterization, which will be compared in the two study groups.

The preparedness tool results will be compared between the two groups as a secondary analysis.

d. Procedures Involved in the Research

**Standard procedural education.** Standard procedural education for all patients undergoing cardiac catheterization at our site formally comes from two sources. First, it is provided verbally by clinical personnel, including physicians and nurses, during routine clinical interactions (i.e. at the time of office visits) and during subsequent phone calls made by the patient to clinical personnel requesting additional procedural information. Second, clinical personnel provide all patients with an information sheet that describes cardiac catheterization (attached as Appendix A; also available online at [www.kramesondemand.com](http://www.kramesondemand.com)).

**Virtual reality.** The VR experience developed for this study will be provided to participants by study personnel using a smartphone (Moto G, Motorola, Schaumburg, Illinois) and a viewer headset (View-Master, Mattel, Segundo, California). This interactive VR experience was filmed using a commercially available camera (360fly 4K, 360FLY, Pittsburgh, Pennsylvania) and developed using proprietary software by Carnevale Interactive (Grand Rapids, Michigan). The VR simulation will allow participants to experience aspects of their procedural day, starting with arrival in the lobby of the catheterization center. The simulation will progress to the catheterization laboratory registration and waiting room, followed by the pre-procedural holding area and finally the procedure room. In each location, the participant will be able to virtually explore the space and have the option of clicking on certain objects of interest, which will trigger an audio description of the object and its purpose.

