### During the procedure

- Hair may be trimmed where the catheter will be inserted.
- You may be given medicine to relax before the procedure.
- You will receive a local anesthetic to prevent pain at the insertion site.
- A healthcare provider inserts a tube called a sheath into a blood vessel in your groin or arm.
- Through the sheath, a long, thin tube called a catheter is placed inside the artery. The catheter is then guided toward your heart.
- To do different tests or check other parts of the heart, the healthcare provider inserts a new catheter or moves the catheter or X-ray machine. For some tests, a contrast dye is injected through the catheter.

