**DIRECTIONS:**

A number of statements which people have used to describe themselves are given below. Read each statement and then circle the appropriate number to the right of the statement to indicate how you feel *right now*, that is, *at this moment*. There are no right or wrong answers. Do not spend too much time on any one statement but give the answer which seems to describe your present feelings best.

	1	2	3	4
1. I feel calm .....	1	2	3	4
2. I feel secure .....	1	2	3	4
3. I am tense .....	1	2	3	4
4. I feel strained .....	1	2	3	4
5. I feel at ease .....	1	2	3	4
6. I feel upset .....	1	2	3	4
7. I am presently worrying over possible misfortunes .....	1	2	3	4
8. I feel satisfied .....	1	2	3	4
9. I feel frightened .....	1	2	3	4
10. I feel comfortable .....	1	2	3	4
11. I feel self-confident .....	1	2	3	4
12. I feel nervous .....	1	2	3	4
13. I am jittery .....	1	2	3	4
14. I feel indecisive .....	1	2	3	4
15. I am relaxed .....	1	2	3	4
16. I feel content .....	1	2	3	4
17. I am worried .....	1	2	3	4
18. I feel confused .....	1	2	3	4
19. I feel steady .....	1	2	3	4
20. I feel pleasant .....	1	2	3	4

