**DIRECTIONS**

A number of statements which people have used to describe themselves are given below. Read each statement and then circle the appropriate number to the right of the statement to indicate how you generally feel.

	NEVER	SOMETIMES	ALMOST ALWAYS
21. I feel pleasant.....	1	2	3
22. I feel nervous and restless.....	1	2	3
23. I feel satisfied with myself.....	1	2	3
24. I wish I could be as happy as others seem to be.....	1	2	3
25. I feel like a failure.....	1	2	3
26. I feel rested.....	1	2	3
27. I am "calm, cool, and collected".....	1	2	3
28. I feel that difficulties are piling up so that I cannot overcome them.....	1	2	3
29. I worry too much over something that really doesn't matter.....	1	2	3
30. I am happy.....	1	2	3
31. I have disturbing thoughts.....	1	2	3
32. I lack self-confidence.....	1	2	3
33. I feel secure.....	1	2	3
34. I make decisions easily.....	1	2	3
35. I feel inadequate.....	1	2	3
36. I am content.....	1	2	3
37. Some unimportant thought runs through my mind and bothers me.....	1	2	3
38. I take disappointments so keenly that I can't put them out of my mind.....	1	2	3
39. I am a steady person.....	1	2	3
40. I get in a state of tension or turmoil as I think over my recent concerns and interests.....	1	2	3

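### Should the plan fix or record the order of the procedure-day STAI and any relaxing medicine?

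*Combined protocol and SAP*

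**What the plan says.** Section 8c (Study Endpoints) defines the outcome by its nearness to the procedure: "The primary outcome of this study is the anxiety level measured just prior to catheterization". Section 8d (Visit 2 – Procedure Day) gives the place and the order: "Study personnel will meet participants in their Prep/Recovery room prior to their procedure and the STAI assessment will be administered to all". Neither mentions medicine given on the day.

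The possibility of such medicine comes from the standard education material. Section 8d says that "clinical personnel provide all patients with an information sheet that describes cardiac catheterization". That sheet is Appendix A, which states, under its heading for what happens during the procedure, "You may be given medicine to relax before the procedure".

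Appendix B contains two STAI forms. The directions for Y-1 ask the respondent to "give the answer which seems to describe your present feelings best". Those for Y-2 ask the respondent "to indicate how you generally feel". The plan does not name the form that supplies the primary score.

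Two sentences list the data. Section 8d: "The data collected for this study entails the State-Trait Anxiety Inventory results, wellness self-assessments results, preparedness survey results and meta-data results". Section 8e (Data Management) names the surveys "as well as demographic and medical history data (for general reporting purposes"). Neither names procedure-day medicine, although the meta-data item is undefined. The psychotropic exclusion in section 8b covers current or long-term use, not medicine given in the catheterization laboratory.

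**The concern.** The comparison of anxiety just before catheterization is naturally read as one of state anxiety, form Y-1. That form asks about the present moment, so a medicine given to relax the patient acts directly on what it measures. If some participants received it before completing the form, their scores would partly reflect the medicine. A real VR benefit might then look smaller, and the listed data would not show how often this happened.

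The paired test in section 9b, of anxiety before and after VR, looks more exposed. The STAI is given only at the off-site baseline visit and on procedure day, so the pair spans the time in which medicine could be given. With no comparison arm, a fall caused by medicine could be credited to VR.

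One sentence in Visit 2 and two or three data fields would seem to settle both points.

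**Working it through.** **1. The plan's own figure.** Section 9a gives effect size 0.5, 90% power, significance level 0.05 and a two-sample t-test; section 8d gives 1:1 allocation. The two-sided noncentral-t calculation needs 85.03 per group, rounded up to 86, as stated. Power at 86 per group is 90.3%. The sample size is sound on its own inputs.

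**2. What the documents establish about medicine before the STAI.**
- Appendix A says that medicine may be given. It gives no frequency, agent or time.
- The sentence stands between hair trimming and the local anesthetic, not in the sheet's own section on preparation before the procedure.
- The sheet is a general commercial leaflet that also covers emergency catheterization for a suspected heart attack. Section 8a screens outpatients from the laboratory schedule.
- The STAI is given in the Prep/Recovery room.

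Medicine before the STAI is therefore possible, but it is not documented for any participant.

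**3. Effect on the randomized comparison.** Let a share *f* of both arms be medicated first, and let a fraction *L* of the VR effect be lost in them, with the SD unchanged. The effect becomes d = 0.5 × (1 − f × L). The documents supply neither *f* nor *L*; the values below are assumptions. Each cell gives d and the power at 86 per group, two-sided alpha 0.05.

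| f | L = 0 | L = 0.5 | L = 1 |
|---|---|---|---|
| 0% | 0.50, 90.3% | 0.50, 90.3% | 0.50, 90.3% |
| 10% | 0.50, 90.3% | 0.475, 87.2% | 0.45, 83.5% |
| 20% | 0.50, 90.3% | 0.45, 83.5% | 0.40, 74.2% |
| 30% | 0.50, 90.3% | 0.425, 79.1% | 0.35, 62.6% |

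The L = 0 column is the case in which medicine lowers scores equally in both arms. There is also no loss if the planned 0.5 already allows for usual use of medicine.

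**4. Unequal use.** Suppose that controls are medicated 10 percentage points more often and the medicine lowers anxiety by 0.3 to 0.8 SD (again assumed). The contrast becomes 0.5 − 0.10 × 0.3 = 0.47, down to 0.5 − 0.10 × 0.8 = 0.42, with power 86.5% to 78.2%. If that difference arises because VR calmed patients, it is a consequence of assignment and belongs in the all-randomized effect. Adjusting for it would condition on a post-randomization variable.

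**5. The paired test.** Its two STAIs differ in place (off site, then the Prep/Recovery room) and in nearness to the procedure (up to several weeks, then the same day; section 8d puts average participation at under one month). It has no control arm. It could not isolate a VR effect even if no one received medicine, so the share medicated would not repair it. Section 8c does not list it among the endpoints.

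**6. What recording or reordering would change.** Recording leaves the primary test, its sample size and its result as they are. If none of 86 recorded participants had medicine first, the one-sided 95% upper bound on the share would be 1 − 0.05^(1/86) = 3.4%; for none of 172, 1 − 0.05^(1/172) = 1.7%. These are descriptive statements about a result not yet seen; they do not measure harm from the omission. Reordering would place the STAI somewhat earlier for later participants than for those already completed, while section 8c defines the outcome by its nearness to catheterization.

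**The case for a change.** The best argument for a change is that the omission is real and cheap to close. The text does not order the STAI against relaxing medicine, the listed data do not show whether any was given, and Y-1 is the kind of measure that responds to it. If nobody is medicated first, a record would let the sponsor say so.

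Most of that stands as a description of the gap, but it does not show that the planned analysis goes wrong. The argument needs Y-1 to be the primary score, which is the sensible reading although the plan does not state it. It also needs a site practice for which the documents offer only a permissive leaflet sentence.

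The cost is more than a sentence and a few fields. Section 8e describes collection from participants on paper tools, and section 8d shows that enrolment had begun before randomization moved to REDCap. Searching the records of completed participants would be a new data source and new staff work, with incomplete results. Conversely, staff already review medical records for screening, so some of the information may be recoverable if a question arises, without any amendment.

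**Conclusion.** No change is needed. This is a gap in operational detail that leaves the primary comparison valid: randomization balances usual care in expectation, and any difference in medicine that follows from assignment is part of the effect being estimated. What remains is possible dilution, from none (90% power) to an amount the documents cannot fix. The lower figures depend on assumed shares of 10% to 30% and on partial or complete loss of the VR effect in those patients. The paired test is limited by its lack of a control arm, with or without medicine.

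The team may choose to note the STAI time and any preceding relaxing medicine and describe them by arm. That would aid interpretation but would alter no planned result. Moving the STAI trades one uncertainty for a mid-trial shift in when the primary outcome is measured, and the evidence here does not justify that. The conclusion would be different if site records showed that medicine commonly precedes the questionnaire.
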